1.9 Summary Table of Endpoints

Endpoints	Timepoint(s) of evaluation of this endpoint

Confidential Page 17 of 30

EARNEST	Protocol No:	Sponsor:	Imperial	College	V1.0 7 th Oct 2024
	174766	London			

	174766	London					
Primary	Time to first related mort AND/OR ser permanent r deficit AND/opermanent cardiorespira	ality vere neurological OR severe	Throughout follow up from randomisation until the first composite event. Patients censored if there is a competing event (non-aortic-related death, patient withdrawal or end of the study). Reported when all patients are five years after randomisation.				
Secondary Aortic-related mortality		until the aortic-recensored if there (non-aortic-relate withdrawal or enwhen all patients year for the TEV.	w up from randomisation elated death. Patients is a competing event ed death, patient d of the study). Reported have completed one AR group and five years ion for all patients.				
	All-cause mo	ortality	until death from a when all patients year for the TEV	w up from randomisation any cause. Reported have completed one AR group and five years ion for all patients.			
	Complication stroke, para cardiorespira	plegia and	patients have co	w up. Reported when all mpleted one year for the nd five years after or all patients.			
	Reinterventi	ons		w up. Reported when all mpleted one and five omisation.			
QoL			allocation, and a months and then randomisation ur	seline prior to group t 6 weeks, 6 months, 12 a annually from ntil the end of follow up. essed using EQ-5D-5L			
	Aortic remod	delling	measured using	TEVAR in the pand at five years CT/MRI scans assessed ranalysis protocol from			

Confidential Page 18 of 30

EARNEST	EARNEST Protocol No: 174766		Imperial	College	V1.0 7 th Oct 2024	
		Health resource use and costs will be measured across follow up assessments and will be analysed at 5 years				
	Cost-effectiveness.		Health resource use and costs will be measured across follow up assessments and will be analysed at 5 years			
	blood	Blood possible baseline 6 weeks annually	ressure we prior to go, 6 month	vill be recorded at group allocation, and at as, 12 months and then adomisation until end of alysed at 5 years.		

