All patients will be seen at 6-weeks, 6-months, one year and yearly (to five years after enrolment) when clinical and cost-effectiveness data will be collected. Both groups will undergo CT/MRI assessment at one year and yearly (to five years after enrolment).

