4.4 Visit Schedule

Visit	0	1	2	3	4	5-9
	Screening	Consent	FOR TEVAR+BMT+ SURV only TEVAR Intervention	Clinical and research assessment	Clinical and research assessment	Clinical and research assessment
TIMEPOINT	Within 3 months of index uTBAD	After the requirement for intensive care or high dependency care has ended, and the patient has not received opiate analgesia for at least 48 hours and from 10 days to 3 months of	10 days-3 months after index uTBAD	FOR BMT+SURV 6 weeks after discharge from hospital admission for the index event c (±14 days) FOR TEVAR+BMT+ SURV	6 months after randomisation (±30 days)	1 year and yearly to 5 years after randomisation. (±30 days)

Confidential Page 24 of 30

EARNEST	Protocol No:	Sponsor:	Imperial	College	V1.0 7 th Oct 2024
	174766	London			

		II.		Į.		
		index uTBAD, noting TEVAR must be performed in 3 months after index event		6 weeks after TEVAR ^c (±14 days)		
Inclusion & exclusion criteria	Х	X				
Informed consent		x				
Demography		X				
Medical history		X		X	x	x
Clinical assessment		x		x	x	x
Clinical details of uTBAD admission		x				
Blood pressure ^a		x	x	x	x	x
CTA aorta		Х		Xp		X
Site report of CT Aorta		X		X		X
Transfer of CT to core lab		X		X (six weeks after discharge from hospital after index event OR six weeks after TEVAR)		X, at 1 and 5 years only
EQ-5D-5L		X		x, measured before imaging results are relayed to the participant	x, measured before imaging results are relayed to the participant	x, measured before imaging results are relayed to the participant
Procedural details			X			
Health resource use, from NHS and personal and social care				x	x	х
Document re- intervention				X	X	x
Document adverse events			X	X	X	х

Confidential Page 25 of 30

EARNEST	Protocol No: 174766	Sponsor: London	Imperial	College	V1.0 7 th Oct 2024

^aStandardised BP measurement: This will be measured using standard protocols. At each visit, three BP recordings will be measured in the sitting position using a validated semi-automated device after at least ten minutes rest. The mean of the second and third readings will be used in analyses. Smoking or vaping will not be permitted for 30 minutes before BP measurement.

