4.5 Follow-up

Follow up visits will take place at each of the sites in a clinical examination room for interview, examination, BP readings and required questionnaires to be completed. Each study visit will be expected to take less than one hour including rest periods for the subject.

Data will be collected on electronic case report forms using a study database called Sealed Envelope which is a regulatory-compliant database and is sponsor-approved for non-CTIMP studies.

Participants will be consented for the central study team to access routinely collected healthcare data, confirming whether the patient has had additional procedures/hospital admissions during the follow up period. Consent will also allow for identifiable data to be linked with the national databases including the National Vascular Registry data, Hospital Episode Statistics data (in England), CHI data, Electronic Data Research and Information Service DRIS (in Scotland) and from the Office of National Statistics. The identifiable fields (NHS number) required for linkage will be encrypted using a one-way encryption algorithm. We will ask patients if they are happy to give consent for their health status to be followed up over time. This will be done by linking the patient's identifiable data with records held by the NHS and maintained by the NHS Information Centre and the NHS Central Register, or any applicable NHS information system. This will allow us to track what happens after the study finishes and observe if anyone gets further tests/investigations and treatment they may have.

As uTBAD may not develop for many years, we will also ask patients to give consent for us to keep personal data stored or accessed for 15 years on the NHSCR (National Health Service Care Register) so that data from national registries can be evaluated. For instance, long-term survival information to be flagged through national registries, for example NHS Digital (previously the Health and Social Care Information Centre); Office of National Statistics (ONS) in England/Wales; General Register Office in Scotland; Hospital Episode Statistics (HES) or Office for Health Improvement & Disparities

Confidential Page 26 of 30

^b If the participant has already undergone a scan at 6 weeks prior to randomization, ie. The patient has been randomised after 6 weeks from discharge, an additional clinical 6 week scan will not be required. All images should however be transferred to the core laboratory

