- In addition to the above ITT analysis, a per-protocol population (PP) will also be defined, which will include all eligible randomised participants according to the treatment received but will exclude major protocol violations. Results from both the ITT and the PP analyses will be presented.
- In an RCT, we do not expect substantial amounts of missing baseline measurements. Therefore, the primary analysis will include complete cases only. However, analysis of the primary outcome and key secondary outcomes could be repeated after using Chained Equations to impute missing baselines multiple times, with resulting estimates of the treatment effects combined using Rubin's rules. This method will be used if more than 10% of cases have some missing baseline data. The method assumes that the incomplete baselines are Missing at Random conditional on measurements that are observed, an untestable assumption.
- The primary outcome analysis assumed non-informative censoring for those participants who did not have the primary outcome during follow up. We will repeat the analysis using inverse probability of censoring weights to adjust for differences between fully observed and censored survival times.

Confidential Page 36 of 30

EARNEST	Protocol No:	Sponsor:	Imperial	College	V1.0 7 th Oct 2024
	174766	London			

- We will consider sub-distribution hazard ratios for the primary outcome to adjust for competing risks such as death from non-aortic causes.
- Other sensitivity analyses will be completed should the trial data or analysis be deficient in another way.

(vi) Cost effectiveness

Cost-utility analysis will consider NHS and personal social services (PSS) costs including productivity losses due to sick leave. The outcomes will be presented as incremental cost per Quality Adjusted Life Year (QALY) gained.

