9.4 Data Collection

Details of procedures for CRF/eCRF completion will be provided in a study manual.

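### The cost-utility analysis counts sick-leave productivity losses as NHS and PSS costs, so its cost per QALY as written would not be an NHS/PSS ratio, and no sick-leave item is listed in the visit schedule

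*Protocol*

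**What the plan says.** Section 7.3 (vi) gives the economic evaluation two sentences. The first sets the cost scope: "NHS and personal social services (PSS) costs including productivity losses due to sick leave". The second sets the result: "The outcomes will be presented as incremental cost per Quality Adjusted Life Year (QALY) gained". No primary perspective is named, and no second, wider analysis is mentioned.

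The data-collection text is narrower:

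- Section 4.4, Visit Schedule, has one economic row, "Health resource use, from NHS and personal and social care", marked at 6 weeks, 6 months, 1 year and yearly to 5 years.
- Section 1.9, Summary Table of Endpoints, describes both costs and cost-effectiveness in the same words: "Health resource use and costs will be measured across follow up assessments and will be analysed at 5 years".
- Section 2.1, Design, refers to the follow-up visits as the time "when clinical and cost-effectiveness data will be collected", without itemising the data.
- Section 4.5, Follow-up, describes access to routine healthcare data for "confirming whether the patient has had additional procedures/hospital admissions during the follow up period", and linkage to health and survival records.
- Section 9.4, Data Collection, says "Details of procedures for CRF/eCRF completion will be provided in a study manual".

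**The concern.** The word joining the two parts of the cost definition places lost work time inside a health and social care payer's budget, where it does not belong. The sentence therefore mixes two perspectives under the name of the narrower one. The result could not be compared with other NHS/PSS ratios, and a reader who took it for a wider-perspective result would have no statement to that effect.

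Sick leave also appears nowhere in the protocol's list of what is collected. Follow-up lasts at least five years, and work absence that is not asked about at visits is hard to reconstruct later. The routine sources described cover health care and survival, not employment.

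The hypothesis in section 1.5 includes cost-effectiveness. The primary aim stated directly after it does not, and sections 1.6, 1.8 and 1.9 class costs and cost-effectiveness as secondary. What is at stake is the meaning of a secondary result that is likely to be used in adoption decisions.

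**Working it through.** The protocol states no cost, QALY difference, cost per QALY or threshold, so there is no figure to reproduce. The check has two parts.

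**1. Sections side by side**

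| Place | Cost scope | Sick leave or work absence? |
|---|---|---|
| 7.3 (vi) | NHS and PSS, with productivity losses counted inside | Yes, as a cost |
| 4.4 | NHS, personal and social care resource use | Not listed |
| 1.9 | Health resource use and costs | Not listed |
| 2.1 | Cost-effectiveness data, not itemised | Not stated |
| 4.5 | Procedures, admissions, survival | Not listed |
| 9.4 | Completion detail left to a manual | Cannot be seen |

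Sections 4.4 and 1.9 describe a health and social care scope, and 7.3 (vi) a wider one. Sections 2.1 and 9.4 leave room for an unlisted question on a form.

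**2. Effect on the ratio**

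Let ΔH be the between-arm difference in mean NHS/PSS cost, ΔP the difference in mean productivity cost, and ΔQ the difference in mean QALYs, all TEVAR minus control.

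- NHS/PSS ratio = ΔH / ΔQ
- Ratio as written = (ΔH + ΔP) / ΔQ
- Shift = (ΔH + ΔP) / ΔQ − ΔH / ΔQ = ΔP / ΔQ

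The shift is zero if mean productivity cost is the same in both arms. Otherwise its sign follows that of ΔP (for ΔQ > 0).

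The protocol gives reasons for ΔP to go either way. The TEVAR arm has an early procedure with a high-dependency stay (5.1). The control arm has the higher assumed 5-year risk of later intervention, 26.5% against 16.7% (7.1). There is no upper age limit (3.1) and no employment rate, so the number of participants with any sick leave to lose is unknown.

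To show sensitivity only, **assume** ΔP between −£2,000 and +£2,000 per participant and ΔQ between 0.1 and 0.3. None of these values is in the protocol.

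- ΔQ = 0.1: shift from −2,000 / 0.1 = −£20,000 to +2,000 / 0.1 = +£20,000 per QALY
- ΔQ = 0.3: shift from −2,000 / 0.3 ≈ −£6,700 to +2,000 / 0.3 ≈ +£6,700 per QALY
- ΔP = 0: no shift at any ΔQ

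If sick leave is collected, the ratio as written moves by ΔP / ΔQ. If it is not, ΔP cannot be computed and the analysis cannot be carried out as described. The sentence needs changing in both cases.

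**The case against.** The strongest defence is that section 7.3 (vi) is an outline. It says what the analysis will consider, not that only one ratio will be shown, and the details of perspective are commonly settled in an analysis plan, which is not at hand. A wider perspective that includes productivity is legitimate. The row in 4.4 is a heading rather than the questionnaire, 2.1 promises cost-effectiveness data without itemising them, and 9.4 leaves form completion to a manual. A work-absence question is compatible with all of these.

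Much of this stands, and it blocks three stronger readings that a reader might infer:

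- *That the base-case cost per QALY would be wrong.* The protocol defines no base case, and including productivity losses is not an error if the perspective is declared and the result reported separately.
- *That sick leave is not collected.* The text supports only that it is not listed.
- *That the distortion is large, or runs in a known direction.* Any figure rests on assumed inputs, and the shift may be nil or of either sign.

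The two parts of the point also cannot both bite on the ratio: data that are not collected cannot distort it.

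The defence does not rescue the sentence itself. This is not detail left for later; it is a stated cost definition that puts a non-NHS, non-PSS item inside the NHS/PSS total. An analysis plan that produced a true NHS/PSS ratio would have to depart from it.

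**Conclusion.** The point holds in limited form. The cost total in 7.3 (vi) is mislabelled, and a ratio built on it would be neither an NHS/PSS ratio nor a declared wider-perspective one. The definition also does not match the data items listed in 4.4 and 1.9. Neither conclusion needs an assumption beyond the ordinary meaning of NHS and PSS costs.

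The numerical consequence is ΔP / ΔQ, with both terms unknown. The illustrated range shows only that the ratio could be sensitive to the choice; it predicts nothing and should not be used to grade the point. The correction is worth making because it changes what the ratio means and costs very little. The effect is confined to a secondary endpoint. The primary time-to-event analysis, type I error, sample size and power are untouched.

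**What to change.** Reword section 7.3 (vi) along these lines: *The incremental cost per QALY will be reported from an NHS and PSS perspective, without productivity losses. Productivity losses from sick leave will enter only a separate analysis, labelled as taking a wider perspective.*

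Then choose one of two routes:

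1. **Keep the wider analysis.** Confirm that the resource-use form already asks about work absence, or add one question, and list the item in the section 4.4 schedule and the section 1.9 table. This should be in place before follow-up starts, since absence not recorded at visits is hard to recover.
2. **Drop it.** Delete the reference to productivity losses; the existing rows in 4.4 and 1.9 then match the analysis as they stand.

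The cost is one reworded sentence and, on the first route, at most one question on an existing form and a line in each of two tables. No additional visits or participants are needed.

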8. REGULATORY, ETHICAL AND LEGAL ISSUES

8.1 Declaration of Helsinki

The investigator will ensure that this study is conducted in full conformity with the seventh revision (2013) of the 1964 Declaration of Helsinki.

8.2 Good Clinical Practice

The study will be conducted in accordance with the guidelines laid down by the International Conference on Harmonisation for Good Clinical Practice (ICH GCP E6 guidelines).

8.3 Research Ethics Committee (REC) Approval

(i) Initial Approval

Prior to the enrolment of participants, the REC must provide written approval of the conduct of the study at named sites, the protocol and any amendments, the Participant Information Sheet and Consent Form, any other written information that will be provided to the participants, any advertisements that will be used and details of any participant compensation.

(ii) Approval of Amendments

Proposed amendments to the protocol and aforementioned documents must be submitted to the REC for approval as instructed by the Sponsor. Amendments requiring REC approval may be implemented only after a copy of the REC's approval letter has been obtained.

Amendments that are intended to eliminate an apparent immediate hazard to participants may be implemented prior to receiving Sponsor or REC approval. However, in this case, approval must be obtained as soon as possible after implementation.

Please Note: Amendments must be submitted to the Funder for review prior to REC submission.

Confidential Page 37 of 30

EARNEST	Protocol No: 174766	Sponsor: London	Imperial	College	V1.0 7 th Oct 2024
	174700	London			

(iii) End of Trial Notification

The REC will be informed about the end of the trial, within the required timelines. The end of trial notification will be submitted within 90 days of the end of trial definition being met.

8.4 HRA approval

Health Research Authority (HRA) approval will be obtained prior to starting the study. Each participating site will confirm capacity and capability prior to commencing.

The HRA and all participating sites also need to be notified of all protocol amendments to assess whether the amendment affects the institutional approval for each site.

8.5 Other Required Approvals

Investigators must ensure that all procedures that take place as part of the trial (either early TEVAR in the subacute phase or late interventions due to complications) are compliant with the Ionising Radiation (Medical Exposure) Regulations, and appropriate review by a Medical Physics Expert and Clinical Radiation Expert has been undertaken.

In the event an extension is required, the relevant approvals will be sought.

The study must also receive confirmation of capacity and capability from each participating NHS Trust before accepting participants into the study or any research activity is carried out. The study will be conducted in accordance with the recommendations for physicians involved in research on human subjects adopted by the 18th World Medical Assembly, Helsinki 1964 and later revisions.

8.6 Non-Compliance and Serious Breaches

All protocol deviations and protocol violations will be reported via the eCRF/CRF and reviewed by the Chief Investigator and reported to the ICTU QA Manager on a monthly basis. Protocol violations will be reported to the Sponsor.

An assessment of whether the protocol deviation/violation constitutes a serious breach will be made. A serious breach is defined as:

A breach of the conditions and principles of GCP in connection with a trial or the trial protocol, which is likely to affect to a significant degree:

- The safety or physical or mental integrity of the UK trial participants; or
- The overall scientific value of the trial

The Sponsor will be notified within 24 hours of identifying a likely Serious Breach. If a decision is made that the incident constitutes a Serious Breach, this will be reported to the REC within 7 days of becoming aware of the serious breach.

Confidential Page 38 of 30

EADNEST	Drotocol No.	Snansarı	Imporial	Callaga	V1.0 7 th Oct 2024
EARNEST	Protocol No: 174766	Sponsor: London	Imperial	College	V1.0 7 Oct 2024

8.7 Insurance and Indemnity and Sponsor

The Sponsor has civil liability insurance, which covers this study in all participating countries (the UK for this study). Imperial College London holds negligent harm and non-negligent harm insurance policies which apply to this study.

8.8 Trial Registration

The study will be registered on a trial database (ISRCTN) in accordance with requirements of the International Committee of Medical Journal Editors (ICMJE) regulations.

8.9 Informed Consent

The consent may only take place once the requirement for intensive care or high dependency care has ended, and the patient has not received opiate analgesia for at least 48 hours.

Consent may be undertaken from 10 days to three months (allowing time for TEVAR to take place if necessary) from the index event.

It will be the investigator's responsibility to obtain written informed consent from the subject after adequate explanation of the aims, methods, anticipated benefits, and potential hazards of the study and before any study procedures are commenced.

Consent will also be obtained for participant's contact details to be shared with the central study team for the purposes of future long-term follow-up and optional dissemination of trial results.

Consent will be obtained for the central study team to access routinely collected healthcare data to confirm whether additional procedures/hospital admissions took place during the follow up period and to obtain long term health outcomes after the study has finished.

The Informed Consent Form will be signed and personally dated by both the subject and the investigator, or a person delegated to do so by the investigator. The subject will be provided with a copy of the signed Subject Information Sheet/Informed Consent Form document. The original Informed Consent Form will be retained with the source documents.

8.10 Contact with General Practitioner

It is the investigator's responsibility to inform the participant's General Practitioner (where applicable) by letter that the participant is taking part in the study provided the participant agrees to this, and information to this effect is included in the Participant Information Sheet and Informed Consent. A copy of the letter should be filed in the Investigator Site File.

Confidential Page 39 of 30

EADNEST	Drotocol No.	Snansarı	Imporial	Callaga	V1.0 7 th Oct 2024
EARNEST	Protocol No: 174766	Sponsor: London	Imperial	College	V1.0 7 Oct 2024

8.11 Monitoring, Audits and Inspections

The investigator shall permit direct access to participants' records and source documents for the purposes of monitoring, auditing, or inspection by the Sponsor, authorised representatives of the Sponsor, NHS, Regulatory Authorities and RECs.

